9.2.2 Source documents

Investigators and study personnel will record clinical data in each patient's source documents (*i.e.*, the patient's medical record). Source documentation will be made available to support the patient research record. Study monitors will review entries on the CRFs at regular intervals, comparing the content with the source documents.

9.2.3 Record retention

The investigator will maintain adequate and accurate records to enable the conduct of the study to be fully documented and the study data to be subsequently verified. After study closure, the investigator should maintain all source documents, study-related documents, and the CRFs. Because the length of time required for retaining records depends upon a number of regulatory and legal factors, documents should be stored until the investigator is notified that the documents may be destroyed. In this study, records are to be retained and securely stored for a minimum of 3 years after the completion of all study-related activities.

9.3 Study Monitoring and Quality Assurance

This is a DSMP Level II study under the Johns Hopkins Sidney Kimmel Comprehensive Cancer Center (SKCCC) Data Safety Monitoring Plan (12/6/2012) Data Monitoring of this protocol will occur on a regular basis with the frequency dependent on the rate of subject accrual and the progress of the study. The protocol will be monitored internally at SKCCC by the Principal Investigator and

externally by the SKCCC CRO in accordance with SKCCC guidelines. Trial monitoring and reporting will be done through the Safety Monitoring Committee (SMC) at SKCCC.

Additionally, scheduled meetings will take place monthly and will include the protocol principal investigator, research nurse, data manager, and, when appropriate, the collaborators, subinvestigators, and biostatistician involved with the conduct of the protocol.

During these meetings the investigators will discuss matters related to: safety of protocol participants, validity and integrity of the data, enrollment rate relative to expectation, characteristics of participants, retention of participants, adherence to protocol (potential or real protocol violations), data completeness, and progress of data for secondary objectives.

10. STATISTICAL CONSIDERATIONS

10.1 Study Design and Sample Size

This is a single-center, single arm, open-label phase II study evaluating the safety, anti-tumor effect, and immunogenicity of neoadjuvant MGA271 given weekly for 6 doses beginning 50 days prior to radical prostatectomy in men with high-risk localized prostate cancer. Our primary objective is to characterize safety, tolerability, and feasibility of treatment of men with Enoblituzumab in the neoadjvuant setting. The trial will monitor toxicity and safety, as well as surgery related adverse events. (see Section 10.2.1). The secondary objective will be to evaluate immune response consistent with the agent's proposed mechanism of action (MOA), antibody-dependent cellular cytotoxicity (ADCC). Tumor cell death will be quantified by Caspase 3 staining, and post-treatment apoptotic index compared with that from the pre-treatment biopsy. The sample size is driven by detecting a pharmacodynamic effect of the agent based on the key secondary endpoint of tumor cell death. A biologically meaningful treatment effect will be deemed to be one where the tumor cell apoptosis is two-fold higher after MGA271 therapy. Previous study showed that baseline apoptosis, measured by Caspase staining, is 0.06 + - 0.08 (Mean + - SD) for Gleason 4 and 0.2 ± 0.2 for Gleason 3 (Kim et al. 2016). Based on this data, we assume that the coefficient of variation of tumor cell death measure is 1.2 and the correlations between the measures pre- and post-treatment is moderate at 0.4, 16 subjects will provide 88% power to detect a 2-fold increase in apoptotic tumor cells after the treatment compared to baseline, using a one-sided paired t-test with significance level 0.05.

In Amendment 1, the study was expended to enroll an additional 16 patients for a total of 32 patients to continue evaluating safety and better estimate the clinical benefit of Enoblituzumab in terms of undetectable PSA level (<0.1 ng/mL) at 12 months following radical prostatectomy.

Patients will be replaced if they are removed from the study after signing the informed consent but before undergoing radical prostatectomy. Patients receiving at least one dose of the study drug will be included in both safety and efficacy analyses.

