5.6 Duration of Therapy

Participation in this study will be terminated for any of the following reasons listed below:

- the patient decides to withdraw from the study (withdrawal of consent) due to unacceptable toxicities or for any other reason
- the patient completes all of the protocol procedures and follow-up requirements
- there are adverse events that, in the judgment of the investigator, may cause severe or permanent injury or are incompatible with continuation on study
- there are major violations to the study protocol or the patient is noncompliant with treatments, as judged by the investigator
- the patient experiences concurrent illness or a change in his condition that, in the judgment of the investigator, renders him unacceptable for further treatment on study
- the patient dies
- the patient is lost to follow-up
- the study is prematurely terminated for safety or feasibility concerns or other reasons

Patients should be removed from the study when any of the above criteria are met. Because an excessive rate of withdrawals can render the study uninterpretable, unnecessary withdrawal of patients should be avoided if possible. When a patient leaves the study early, the investigator should make every effort to contact the patient and to perform the final follow-up evaluation (even by telephone interview). The reason for removal of a patient from the study, and the date of removal, must be appropriately documented.

Patients will be replaced if they are removed from the study after signing the informed consent but before undergoing radical prostatectomy. Patients receiving at least one dose of the study drug will be included in safety analyses, and those also undergoing prostatectomy will be used for the efficacy analyses.

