8.2 Primary Endpoint

8.2.1 Rate of adverse events

All subjects receiving at least one dose of the study drug will be evaluated for safety by monitoring symptoms, physical examinations, and laboratory tests. Adverse events will be classified and graded according to the NCI Common Toxicity Criteria version 4.0 (see Appendix B). The absolute number and frequency of each adverse event will be reported, and subdivided according to toxicity grade. A description of adverse events by treatment arm will also be reported. A particular adverse event occurring more than once in the same subject will be counted only once and at its worse grade.

- 8.2.2 In expansion cohort (amendment 1):
 - All subjects receiving at least one dose of the study drug will be assessed for PSA₀ Response Rate (Undetectable PSA level <0.1 ng/mL) at 12 months following radical prostatectomy

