Our primary efficacy endpoint will be to estimate the clinical benefit of neoadjuvant Enoblituzumab in terms of undetectable PSA level (<0.1 ng/mL) at 12 months following radical prostatectomy. The estimate and corresponding 90% confidence interval based on 32 patients is listed in the table below.

Observed N with undetectable PSA	Observed rate	90% CI
0	0	0% - 7.8%
1	3.1%	0.7% - 12.9%
2	6.2%	2.1% - 17.2%
3	9.4%	3.8% - 21.3%

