10.3 Analysis Populations

10.3.1 Intention-to-treat population

All patients who meet eligibility criteria and receive at least one dose of the study drug will be included in the analysis of the primary and secondary endpoints, even if there are subsequent protocol deviations. However, in cases where prostatectomy is not performed or if adequate surgical tissue is not collected, then determination of the secondary endpoints (apoptosis/proliferation marker analysis, tissue CD8⁺ T cell analysis) will not be possible. Patients will be replaced if they are removed from the study after signing the informed consent but before receiving the study drug.

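### The protocol gives two analysis sets for the 12-month PSA0 primary endpoint and two replacement rules, and no PSA0 outcome for a dosed man who is never operated on

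*Combined protocol and SAP*

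**What the plan says.** Section 10.2.1.1 makes PSA0 (PSA below 0.1 ng/mL one year after prostatectomy) the main efficacy measure: "Our primary efficacy endpoint will be to estimate the clinical benefit of neoadjuvant" enoblituzumab on that scale.

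On who is analysed:

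- Section 5.6 puts dosed men in the safety analyses, and says "those also undergoing prostatectomy will be used for the efficacy analyses".
- Section 8.2.2, the only one of these sections to name PSA0, says "All subjects receiving at least one dose of the study drug will be assessed for" it.
- Section 10.1 says "Patients receiving at least one dose of the study drug will be included in both safety and efficacy analyses".
- Section 10.3.1, headed as the intention-to-treat population, applies this to primary and secondary endpoints alike: "All patients who meet eligibility criteria and receive at least one dose of the study drug will be included in the analysis".

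On replacement, sections 5.6 and 10.1 carry the same sentence: "Patients will be replaced if they are removed from the study after signing the informed consent but before undergoing radical prostatectomy". Section 10.3.1 says instead: "Patients will be replaced if they are removed from the study after signing the informed consent but before receiving the study drug".

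Only section 10.3.1 considers a missing operation: "in cases where prostatectomy is not performed or if adequate surgical tissue is not collected, then determination of the secondary endpoints" is ruled out. The endpoints it lists there are the tissue markers; PSA0 is not among them.

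**The concern.** Take a man who is dosed and then leaves before surgery. Section 5.6 drops him from the PSA0 denominator, while sections 8.2.2, 10.1 and 10.3.1 keep him in (the last provided he was eligible). He is replaced under 5.6 and 10.1 but not under 10.3.1. The sections that keep him do not say what his PSA0 result is, although the 12-month clock starts at an operation he never had.

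Such a man may be missing for reasons linked to treatment. Section 5.6 allows removal for adverse events, and the feasibility rule in section 10.2.1 lists systemic symptoms that interfere with the operation among events possibly attributable to the drug. An operated-only rate would leave those men out of the primary result.

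The synopsis says the estimate is meant to inform the design of larger neoadjuvant trials, so the reader needs to know which rate is being reported.

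**Working it through.** **Passages side by side**

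| Section | Efficacy or PSA0 set | Replaced if removed | Dosed man without surgery |
|---|---|---|---|
| 5.6 | Dosed and operated | Before prostatectomy | Excluded, replaced |
| 8.2.2 | All dosed | Not stated | Included, no outcome given |
| 10.1 | All dosed | Before prostatectomy | Included, replaced, no outcome given |
| 10.3.1 | Eligible and dosed | Before first dose | Included, not replaced, no PSA0 outcome given |

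The eligibility condition in 10.3.1 matters only if an ineligible man is dosed in error, because section 4.1 has eligibility confirmed before treatment. The live conflict is between 5.6 and the other three.

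**Reproducing the plan's table.** Section 10.2.1.1 tabulates 90% intervals for 0 to 3 responders of 32. The Wilson interval with z = 1.645 (z² = 2.706) is

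(p + z²/2n ± z·√[p(1−p)/n + z²/4n²]) / (1 + z²/n).

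For 0/32 the upper limit reduces to z²/(n + z²) = 2.706/34.706 = 7.8%. The other rows come out at 0.7–12.9, 2.1–17.2 and 3.8–21.3. All four match, so Wilson is used below.

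**Effect of the denominator.** Assumptions, none of which the documents supply:

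- x responders;
- k dosed men without surgery;
- those k men scored as non-responders.

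Replacement follows 5.6 and 10.1, so 32 men are operated on. The operated-only rate is x/32 and the all-dosed rate is x/(32 + k), so the gap is

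x/32 − x/(32 + k) = xk / [32(32 + k)].

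For example, x = 20 and k = 4 give 80/1152 = 6.9 points.

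| k | All-dosed rate, x = 20 | 90% interval (%) | Gap in points, x = 3 | x = 16 | x = 20 | x = 24 |
|---|---|---|---|---|---|---|
| 0 | 20/32 = 62.5% | 48.0–75.1 | 0 | 0 | 0 | 0 |
| 1 | 20/33 = 60.6% | 46.3–73.3 | 0.3 | 1.5 | 1.9 | 2.3 |
| 2 | 20/34 = 58.8% | 44.8–71.6 | 0.6 | 2.9 | 3.7 | 4.4 |
| 4 | 20/36 = 55.6% | 42.0–68.3 | 1.0 | 5.6 | 6.9 | 8.3 |

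The k = 0 row is also the operated-only result for every k. Its interval is 75.1 − 48.0 = 27.1 points wide. The range of 16 to 24 responders (50–75%) is guided only loosely by the 30–50% recurrence in section 2.1, which has no time horizon. Three responders is the top row of the plan's own table. If men without surgery are instead not assessable, both denominators are 32 and every gap is zero.

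With non-responder scoring, section 10.1 taken on its own terms has a denominator of 32 + k, so the printed table, built on 32, applies only when k = 0. Larger gaps would arise from joining the 5.6 population to the 10.3.1 replacement rule; no section does that, and they are not claimed.

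**Stopping tables.** If dosed men are replaced, more than 32 may be dosed, but both tables in section 10.2.1 end at 32. Recomputing with the stated rules reproduces every tabulated boundary: toxicity, prior beta(1.5, 5.5), stop if P(risk > 0.33) ≥ 0.65; feasibility, prior beta(1, 9), stop if P(risk > 0.10) ≥ 0.80. Beyond 32 the same rules give:

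- Toxicity: 13 events at n = 33 (posterior 0.656) and 14 at n = 34 to 36 (0.731 at 34, 0.652 at 36; 13 events at 34 give only 0.613).
- Feasibility: 6 events at n = 33 to 36 (0.879 at 33, 0.842 at 36; 5 events at 33 give only 0.760).

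**The case against.** Only section 5.6 is out of line. Section 8.2.2 names PSA0, and 10.1 and 10.3.1 sit in the statistical chapter; all three use dosed men. The Amendment 1 summary of changes lists 8.2.2 as new and shows no change to 5.6, so 5.6 may be left over from before PSA0 became primary. A careful analyst would probably choose the dosed set. That makes the intended set easier to guess, but the contradiction remains, and the synopsis describes the first 16 evaluable patients as men who have surgery, which gives 5.6 some support.

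The effect is also conditional and modest. Surgery must already be scheduled at entry (section 3.2), so few men may miss it; k = 4 has no basis in the documents; and the gaps are well inside the interval width. PSA0 is only estimated, so no decision threshold moves. All of this stands and limits the size of the point.

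Scoring an unoperated man as a non-responder is one defensible choice, and an operated-only primary rate would be another. That is fair. The plan still has to choose, and reporting the other rate as a sensitivity analysis shows what the choice does.

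Men operated on but lost before 12 months are a separate matter, not settled by the change proposed here. Extending the stopping tables is mechanical, since the posterior rules already define the boundary at any sample size.

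**Conclusion.** The concern holds. The current text contradicts itself on the PSA0 analysis set and on replacement, and the sections that keep a dosed but unoperated man assign him no primary outcome. The textual conflict is certain; its numerical effect is not. With replacement as in 5.6 and 10.1, non-responder scoring and 16 to 24 responders, the operated-only rate exceeds the all-dosed rate by 1.5–2.3 points for one man without surgery, 2.9–4.4 for two and 5.6–8.3 for four. The difference vanishes if every dosed man is operated on or if unoperated men are treated as not assessable. Dosed men stay in the safety analysis on every reading. The wording should be settled before PSA0 is analysed, because following 5.6 as written could remove men whose surgery was lost to a possible drug effect.

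**What to change.** Reconcile sections 5.6, 8.2.2, 10.1 and 10.3.1:

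1. For PSA0, use the all-dosed set that 8.2.2 and 10.1 already name, and state that a dosed man without prostatectomy counts as a non-responder.
2. Report the operated-only rate as a declared sensitivity analysis.
3. Confine the surgery condition in 5.6 to the tissue endpoints, and say whether the eligibility condition in 10.3.1 applies to PSA0.
4. Put one replacement rule in 5.6, 10.1 and 10.3.1. Either works for PSA0 provided a replaced dosed man stays in the denominator, and the text should say so.
5. If dosed men are replaced, extend the toxicity table past 32 under its stated rule, and the feasibility table too if men without surgery count in it.

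The cost is a wording amendment with no new data. The headline rate may be slightly lower, and the denominator may exceed 32 if dosed men are replaced.

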10.2 Study Endpoints

10.2.1 Analysis of the primary endpoints

Safety and feasibility

Frequency of adverse events will be described using summary statistics. The proportion of patients with an adverse event will be reported with an exact binomial 95% confidence interval. All subjects receiving at least one dose of the study drug(s) will be evaluable for toxicity.

Early stopping rules for toxicity: Toxicity will be monitored closely and continuously. Any grade-3/4 local reactions (erythema, swelling, pain) attributable to MGA271 or Grade 3 infusion-related reaction or cytokine release syndrome that lasts ≥ 12 hours will be considered AEs for purposes of this stopping rule. A grade 4 infusion related reaction of any duration will be considered AEs for purposes of this stopping rule. If the risk of these adverse events appears to be higher than 33%, we will temporarily halt the study pending dose modification. Specifically, we apply a Bayesian toxicity monitoring rule that suspends the enrollment if the posterior probability of risk being larger than 0.33 is 65% or higher. The monitoring rule uses beta (1.5, 5.5) as prior distribution. This means that our prior guess at the proportion of toxicity is 21%, and there is 90% probability that this proportion is between 3% and 49%. The decision rule for toxicity stopping is as follows:

Study termination if:	3 AEs	4 AEs	5	6	7	8	9	10	11	12	13
In number of patients between:	3 - 4	5 - 7	8 - 10	11 - 12	13 - 15	16 - 18	19 - 21	22 - 24	25 - 27	28 - 30	31- 32

For example, we will interrupt the accrual if 3 patients have AEs among the first 4 receiving treatment. If 4 or more out of the first 5-7 patients have AEs, we will suspend accrual.

The operating characteristics of the stopping rule are shown below and are based on 5000 simulations:

Risk of AE	0.20	0.25	0.30	0.33	0.40	0.45
% of Time study stops	7.5%	18%	33.7%	46%	54.6%	73.3%
Expected sample size	30.3	28.2	25.3	22.8	21.2	17.3

Early stopping rule for feasibility: We do not anticipate an increase in the surgical difficulty with the use of neoadjuvant MGA271. Men who have had acute (post-biopsy) and prolonged issues (chronic prostatitis) with prostate infection/inflammation are fairly routine in urologic surgical practice, and we anticipate that the immune infiltrate potentially induced by MGA271 would not pose a substantial increase in surgical difficulties. However, in addition to safety, feasibility will be monitored separately. The feasibility rule for this study will be based on a change in surgical outcomes beyond what may be expected for patients without presurgical interventions and that may be attributable to the study drug. These events would include: (1) average blood loss in excess of 2500 mL, (2) average operative time in excess of 3.5 hours, and (3) average hospital stay in excess of 4 days, (4) systemic symptoms (fevers, rash, myelosuppression) compromising the planned surgery. These values are approximately 2 standard deviations above the average surgical outcomes for men undergoing radical prostatectomy at Johns Hopkins Hospital.

We expect no surgery complication in at least 90% cases. We will monitor this endpoint after every patient. If it becomes apparent that the surgeries are being negatively impacted by the pre-surgical investigational treatments, then the study will be suspended for review. Again, we apply a Bayesian monitoring rule that suspends the enrollment if the posterior probability of complications > 0.10 is 80% or higher. The monitoring rule uses beta (1, 9) as prior distribution, based on the expectation that these treatments will not impact the

feasibility of surgery. Instances where the study would be temporarily suspended are listed below.

Stopping rules:

Not feasible if the observed number of	2	3	4	5	6
surgical complications is:					
In number of patients between:	2 - 6	7 - 14	15 - 22	23 - 30	31 - 32

The operating characteristics of the stopping rule are shown below and are based on 5000 simulations:

Risk of surgical complication	0.025	0.05	0.10	0.15	0.20
% of Time study stops	1.1%	5.9%	29.2%	57.7%	81.4%
Expected sample size	31.7	30.7	26.4	20.9	15.3

10.2.1.1 For expansion Amendment 1

Estimation of PSA₀ Response Rate (Undetectable PSA level <0.1 ng/mL) at 12 months following radical prostatectomy

Our primary efficacy endpoint will be to estimate the clinical benefit of neoadjuvant Enoblituzumab in terms of undetectable PSA level (<0.1 ng/mL) at 12 months following radical prostatectomy. The estimate and corresponding 90% confidence interval based on 32 patients is listed in the table below.

Observed N with undetectable PSA	Observed rate	90% CI
0	0	0% - 7.8%
1	3.1%	0.7% - 12.9%
2	6.2%	2.1% - 17.2%
3	9.4%	3.8% - 21.3%

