2.2.3.2 Clinical Trial Experience

A total of 160 adult patients have received MGA271 at doses up to 15 mg/kg, the maximum dose given in this study. One-hundred and forty-six of these patients received MGA271 in which MGA271 was given alone (no other chemotherapy was administered with MGA271). In other studies, 14 patients received MGA271 in combination with another drug for cancer treatment. To date, no person under the age of 18 has been treated with MGA271.

So far, the most important safety risk that has been identified with MGA271 is infusionrelated reaction (including reactions known as cytokine release syndrome [CRS]). Infusionrelated reactions are effects to a drug that may occur during or shortly after an infusion. Signs and symptoms of an infusion-related reaction may include fever, chills, nausea, vomiting, headache, muscle stiffness, rash, itching, low blood pressure, and difficulty breathing. Infusion-related reactions can be life threatening and, in rare cases, may cause death. Infusion related-reactions have occurred in a total of 37% (about 4 in 10) patients receiving treatment with MGA271. Most of the infusion-related reactions observed in patients receiving MGA271 have been mild to moderate in severity. However, six patients receiving MGA271 (< 4% of patients) have had serious or severe infusion-related reactions. These patients, some of whom were hospitalized for these reactions, recovered after receiving treatment with steroids, antihistamines, intravenous fluids, and other medications. One patient was discontinued from the study after experiencing a moderate infusion reaction.

The following were the most common side effects that were considered related to MGA271 administration and were seen in at least 1 of 10 participants. These side effects have been generally mild or moderate.

- Infusion-related reactions (including CRS) (37%)
- Fatigue (32%)
- Nausea (18%)
- Chills (14%)
- Vomiting (13%)

A total of 18 patients (11% or 1 in 10 patients) have experienced serious or severe side effects that were considered related to MGA271. Serious or severe side effects that occurred in 3 or more patients were infusion related reactions (6 patients, described above) and hyponatremia (which occurred in 3 patients).

There have not been any deaths considered related to the use of MGA271.

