- IV fluids, supplemental oxygen and bronchodilators should be considered as appropriate.
- If symptoms have resolved to baseline within 12 hours, a re-challenge may be considered at the next scheduled dose, with a 50% reduction of infusion rate. In addition, patients should be pre-medicated for this re-challenge and for any subsequent doses of MGA271 with the following: diphenhydramine hydrochloride 25-50 mg IV, oral acetaminophen 625 mg and hydrocortisone 25-100 mg IV. Patients who have a Grade 3 infusion reaction that does not resolve within 12 hours despite medical management should not receive further MGA271.
- Patients who experience a second Grade 3 infusion reaction at the time of rechallenge of MGA271 (irrespective of duration of first Grade 3 reaction), will permanently discontinue MGA271.
- Patients who experience a Grade 3 infusion reaction despite steroid premedication administration should permanently discontinue study drug.
- Report as an Immediately Reportable Event (IRE) within 24 hours.
- Report the event as a SAE, if appropriate.

6.4.4.4 Grade 4:

- Stop the infusion and disconnect the infusion tubing from the patient.
- TO AVOID EXACERBATION OF INFUSION REACTION OR CRS: DO NOT FLUSH THE TUBING.
- Administer diphenhydramine hydrochloride 50 mg IV, methylprednisolone 2-4 mg/kg IV (or more as considered appropriate), and other medications/treatment as medically indicated (e.g., an IL-6 receptor inhibitor or IL-6 inhibitor, an IL-2 receptor inhibitor, and/or an anti-TNF α antibody).
- Give epinephrine or bronchodilators as indicated.
- Support ventilation and blood pressure as indicated.
- Report as an IRE within 24 hours.
- Report the event as an SAE.
- Patients who have a Grade 4 infusion reaction will not receive further MGA271.

6.4.4.5 Grade 5:

- Report as an IRE within 24 hours.
- Report the event as an SAE.

All changes in the infusion of MGA271 including interruption of the infusion and its duration as well as reductions in infusion rate and duration must be recorded.

IRB#: IRB0010377

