6.4.5.2 Grade 3 or 4 AEs

Drug administration should be held upon observation of AEs of \geq Grade 3 severity to enable patient management, monitoring of the resolution of the event, and assessment of the relatedness of the event. An AE of \geq Grade 3 that is considered related to MGA271 will result in discontinuation of therapy unless otherwise specified in the protocol. For AEs associated with liver function test abnormalities, drug administration should also be discontinued for concomitant ALT >3xULN and total bilirubin >2x ULN without an alternative etiology (Hy's Law).

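### The toxicity stopping rule in 10.2.1 counts only local reactions and certain infusion reactions, so it omits grade 5 events and most other related events that end a patient's therapy

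*Combined protocol and SAP*

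**What the plan says.** Under the early stopping rules for toxicity, 10.2.1 of the combined protocol and SAP names the countable events:

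- "grade-3/4 local reactions (erythema, swelling, pain) attributable to MGA271 or"
- "Grade 3 infusion-related reaction or cytokine release syndrome that lasts ≥ 12 hours"
- a third, added in a separate sentence: "A grade 4 infusion related reaction of any duration will be considered AEs for purposes of this stopping rule"

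The limit is tied to that list: "If the risk of these adverse events appears to be higher than 33%, we will temporarily halt the study pending dose modification". The criterion "suspends the enrollment if the posterior probability of risk being larger than 0.33 is 65% or higher", with a beta(1.5, 5.5) prior. The boundary runs from 3 events in 3-4 patients to 13 events in 31-32.

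Elsewhere the protocol treats a wider set of events as ending a patient's therapy. Section 6.4.5.2 says that an adverse event of at least "Grade 3 that is considered related to MGA271 will result in discontinuation of therapy unless otherwise specified in the protocol", and it adds a liver-function criterion. Section 6.4.4.3 says "Patients who experience a Grade 3 infusion reaction despite steroid premedication administration should permanently discontinue study drug", whatever the duration. Section 6.4.2 defines a grade 5 infusion reaction.

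The known safety profile is in 2.2.3.2: of 160 treated patients, 18 had related serious or severe side effects. "Serious or severe side effects that occurred in 3 or more patients were infusion related reactions (6 patients, described above) and hyponatremia" (3 patients). No related death had been seen.

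**The concern.** Safety is a primary objective, and this is the numerical rule written for toxicity. A reader of the 33% limit and the operating-characteristics table would naturally take them to describe protection against drug toxicity. They describe protection against three listed event types.

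Four kinds of related event do not enter the count as the text stands:

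- grade 5 events;
- hyponatremia of grade 3 or higher;
- the liver case in 6.4.5.2, and any other related event of grade 3 or higher that is neither a local nor an infusion reaction;
- a grade 3 infusion reaction despite steroid premedication that lasts under 12 hours.

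If toxicity came mainly from these, several men could have therapy ended for related events while the boundary stayed far away. The prior points to the same mismatch. It is centred on 21% and described as a guess at the proportion of toxicity, whereas serious or severe infusion reactions occurred in under 4% of treated patients.

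**Working it through.** **1. Reproduce the plan's rule.** Inputs from 10.2.1: prior beta(1.5, 5.5), limit 0.33, cut-off 0.65. With r events in n patients the posterior is beta(1.5 + r, 5.5 + n − r), and the boundary is the smallest r with P(risk > 0.33) ≥ 0.65. For example, 3 events in 4 patients give 0.69 (suspend), while 3 in 5 give 0.61 (continue). Every printed boundary entry for n = 3 to 32 reproduces. The prior mean is 1.5/7 = 21.4%, with 5th and 95th percentiles of 3.0% and 49.5%, as stated.

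**2. Reproduce the operating characteristics.** Exact recursion over 32 patients, checking the boundary after each one:

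| Risk of a countable event | Exact P(stop) | Printed |
|---|---|---|
| 0.20 | 7.7% | 7.5% |
| 0.25 | 17.7% | 18% |
| 0.30 | 33.7% | 33.7% |
| 0.33 | 45.4% | 46% |

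The printed values at 0.40 and 0.45 (54.6% and 73.3%) do not reproduce (exact 72.4% and 86.6%). That is a separate matter, and nothing below depends on those two columns.

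**3. Share of known events outside the list.** From 2.2.3.2:

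- Related serious or severe: 18/160 = 11.25%.
- Infusion reactions among them: 6/160 = 3.75%.
- Patients outside infusion reactions: 18 − 6 = 12, and 12/18 = 67%.
- Not itemised: 18 − 6 − 3 = 9, taking the infusion-reaction and hyponatremia patients as distinct.

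The 67% is uncertain in both directions. Some of the nine could have had local reactions, which would lower it. Some of the six could have had grade 3 reactions under 12 hours, or serious reactions below grade 3, which would raise it.

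**4. What the narrow list does to the stopping probability.** Let R be the true risk of any related severe event and s the share that is countable. The rule then sees a risk of R × s. The documents do not give s for this trial, so a range is assumed; one-third corresponds to 6/18.

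| Countable share s | Risk seen at R = 33% | P(stop) |
|---|---|---|
| 20% | 6.6% | 0.2% |
| 33% | 11% | 0.9% |
| 50% | 16.5% | 3.7% |
| 80% | 26.4% | 22% |
| 100% | 33% | 45% |

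**5. Cost of counting more.** With the same boundaries, P(stop) is 0.03% at a risk of 4% (about the infusion-reaction rate) and 0.9% at 11% (about the rate for all related serious or severe effects).

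**The case against.** The strongest reply is that this rule is not the only safeguard and does not claim to cover all toxicity. Much of that stands:

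- The feasibility rule, also in 10.2.1, is a second numerical rule. It counts systemic symptoms that compromise surgery, has a 10% limit, and suspends at 2 events in 2-6 patients.
- Section 7.5.2 requires SAEs to reach the IND sponsor within 24 hours, and fatal, life-threatening or treatment-related ones to reach the IRB within 3 days.
- Section 9.3 provides Safety Monitoring Committee oversight and monthly meetings. Under 11.5 the principal investigator or the medical monitor can have accrual closed.
- Ending one man's treatment and suspending a trial are different decisions and need not use identical events. The 12-hour condition also echoes the re-challenge provision in 6.4.4.3.

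A reader might infer that a drug-related death could never halt the trial. The documents do not support that: 11.5 allows closure on one event, and a fatal infusion reaction might in practice be counted as having passed through grade 4. A reader might also infer that an uncrossed boundary would let the drug be reported as safe. Nothing makes the boundary the safety conclusion. Sections 8.2.1, 10.2.1 and 10.4 report all adverse events by grade, give an exact 95% interval for the proportion of patients with an event, and summarise serious events, withdrawals and deaths separately.

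What remains is that none of these safeguards sets a numerical limit on related toxicity in general, and that 10.2.1 does not explain why its list is so much narrower than 6.4.5.2.

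**Conclusion.** The point holds for the scope of the pre-specified toxicity rule. The rule omits grade 5 and, by type or duration, most of the related toxicity that the protocol itself treats as ending therapy. Its operating characteristics should be read as applying to the listed local and infusion reactions only.

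The size depends on the countable share, which is assumed. At a true total risk of 33% the stopping probability ranges from 0.2% to 22% as that share goes from 20% to 80%, against 45% if everything counted. This takes the event mix as fixed when total risk is about three times the historical 11%, which the documents cannot confirm.

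It would be too strong to say that exactly two-thirds of known severe toxicity is invisible to the rule. The 12 of 18 counts patients, nine of them are not itemised, 14 of the 160 received combination treatment, and serious or severe is not the same as grade 3-5. Nor would a wider list make the rule react to one death, because the boundary needs at least 3 events.

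**What to change.** Reconcile the countable-event definition in 10.2.1 with the therapy-ending criteria in 6.4.4 and 6.4.5.2, in one of two ways:

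1. Count related events of grade 3 or higher that end therapy under those sections, including grade 5, using the protocol's existing standard of events considered related. The prior, 33% limit, 65% cut-off and boundary table stay unchanged.
2. If the narrow list is intended, state in 10.2.1 that the rule and its operating characteristics cover local and infusion reactions only, not overall toxicity, and give the reason.

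In either case, state separately how a single related death is handled at trial level. No rule for treating an individual patient needs to change.

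The cost is an amendment to the wording, with no new data collection. The first route slightly raises the chance of an unnecessary pause: about 0.9% at an 11% risk, against 0.03% at 4%. The second adds no pauses but leaves related toxicity in general without a numerical limit.
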